4.1 Informed Consent

The Principal Investigator or his/her authorized designee will conduct the Informed Consent for performing the procedure – transcatheter PDA closure as per their hospital policy. No special consents are required for the purpose of this clinical study. All participating study sites must obtain center specific IRB approval to enter patient data in the PDA Module. Individual consents from the subjects or legally authorized representative (LAR) is not required unless local laws and governing IRB requirements require obtaining informed consent for data entry to this registry. No deviation of standard clinical practice is expected to participate in this study. No special pre-procedure, post-procedure, and follow-up testing is required for the purpose of this clinical study.

Patients with a weight less than 2 kg will be undergoing transcatheter PDA closures and their protected health information (PHI) will be entered into the PDA module. If there are local IRB rules that involves the need for individual consents from the LAR for sharing PHI, then a separate Informed consent must be obtained using the local IRB approved informed consent in accordance with IRB requirements. The patient under the age of 18 will also be informed about the clinical study within his/her ability to understand. Per state, local, and/or IRB requirements, processes will be followed and documented to collect assent for minor children. The consent will allow for the sharing and transfer of raw patient level data to the sponsor.

4.2 Pre-catheterization Clinical Assessment

The following assessments, diagnostic tests and evaluations and must be included in the PDA module, please see Appendix C for the CRF to be used:

- a. Demographics- including subject's age, gender, ethnicity, birth weight, gestational age
- b. Medical History-

o Indicate subject's primary symptom, associated heart defects and co-morbidities, genetic syndromes if any, ongoing medical support, current medications, history of prior attempted medical or surgical therapy for the PDA

c. Transthoracic echo (TTE) -

o PDA measurements, color and spectral Doppler findings, estimates of pulmonary hypertension, left ventricular function and dimensions, pulmonary and aortic flow and dimensions, aortic arch sidedness, presence of other heart defects, and pulmonic and tricuspid valve regurgitation Baseline assessments must be obtained within 2 weeks of the procedure

4.3 Implant/Procedure

The Amplatzer Piccolo Occluder device can be implanted either transvenously via the femoral vessels. To minimize complications in small infants (< 2 kg) it is recommended to utilize the anterograde transvenous approach via the femoral vein as the preferred approach. The use of invasive hemodynamic measurements and angiograms are not required in this study to minimize complications, and instead whenever possible hemodynamic assessments and visualization of the anatomy may be performed using intra-operative echocardiography. The recommended use of Heparin is considered optional, and not required if the subject is at high risk for bleeding complications, including children

< 2kg.

The following procedural data must be recorded in the PDA module:

- a. Demographics- including subject's age and procedure weight
- b. Procedure data-

o Primary indication for the procedure, anesthesia type, image guidance techniques used, access vessels, hemodynamic assessment, sheath/catheter sizes, PDA morphologic types, intra-procedural PDA measurement by angiography, heparin administration, device delivery technique, contrast and radiation doses, adverse events

c. Device/implant data-

o Device(s) implanted, device size, residual shunting by angiography, grade of residual shunting, peak/mean gradient across left pulmonary artery and aorta (optional)

d. Intra-procedure Transthoracic echo (optional)-

o Baseline PDA size, residual PDA shunting post device implantation, peak/mean gradient across left pulmonary artery and aorta, left ventricular function and dimensions, pericardial effusion, increased tricuspid or pulmonary valve regurgitation.

4.4 Post-Procedure Follow-up

The follow-up assessment must be obtained within 48-hoours, 1-month and 6-months after the procedure. The schedule of all assessments is provided in Appendix E. The following post-procedure follow-up assessments, diagnostic tests and evaluations and must be included in the PDA module:

- a. Demographics- including subject's age, weight
- b. Transthoracic echo (TTE) including checking for the presence of the device within the PDA, degree of residual shunting if any, spectral Doppler findings, estimates of pulmonary

hypertension, left ventricular function and dimensions, pulmonary and aortic flow and dimensions, pulmonic and tricuspid valve regurgitation

Subjects should be on appropriate endocarditis prophylaxis according to the American Heart Association recommendations for prophylaxis.

5 ADVERSE EVENTS

Risks associated with the procedure are managed in accordance with ISO 14971. The risk analysis included an objective review of published and available unpublished medical and scientific data. The sections below provide an overview of residual risks identified in the risk management report and anticipated benefits of the medical device. The additional tests and assessments required by the clinical investigation were analyzed for additional risks to subjects of this clinical investigation, and are incorporated in the sections below.

5.1 Adverse Event Definitions

For details of each adverse events (AE) and definitions, refer to Appendix A.

5.2 AE Reporting Requirements (Adverse Event Form)

Procedural adverse events must be documented carefully. If there is an adverse event that arises directly as a result of the procedure or the device, or noted during follow-up, an Adverse Event Form (**Appendix D, G**) must be filled out separate from the PDA Module and reported to their IRB and Industry Sponsor.

5.3 Specific Adverse Events

The adverse event form includes specific risks associated with transcatheter device closures that needs to be followed. They include:

- a. Access complications: Include site, timing and type of complication, and outcome
- b. Valvular injury: Include site, timing and type of complication, and outcome
- c. Device embolization: Include timing of embolization, embolization site and outcome
- d. Vessel stenosis: Include timing of vessel stenosis, site of vessel stenosis and outcome

5.4 Other Adverse Events

Other risks associated with the implant procedure are similar to those of other cardiac catheterization procedures in infants and children and are documented below:

Air embolism	Allergic drug reaction	Apnea
Allergic dye reaction	Anesthesia reactions	Arrhythmia

Confidential

Arteriovenousfistulae	Hematoma	Pericarditis	
Air embolism	Hemodynamic compromise	Peripheral embolism	
Bacterial endocarditis	Hemolysis	Peripheral pulse loss	
Bleeding at the access site	Hypertension	Pleural effusion	
Brachial plexus injury	Hypotension	Pseudoaneurysm	
Bruising	Infection	Reintervention for device	
Cardiac perforation	Myocardial infarction	removal	
Cardiac tamponade	Nickel sensitization	Radiation injury/burn	
Chest pain	Nickel toxicity	Respiratory distress	
Death	Palpitations	Stroke	
Deep venous thrombosis	Partial obstruction of the	Transient ischemic attack	
Device erosion	Aorta	Thrombosis	
Dissection	Partial obstruction of the	Valve damage	
Embolism	PulmonaryArtery	Vascular occlusion	
Fever	Perforation	Vessel damage/perforation	
Headache/migraine	Pericardial e f f u s i o n	Thrombus f o r m a t i o n	

5.5 Risk Minimization

Every possible effort should be taken to minimize risks. This begins with physician training and proctoring. In addition, each site is encouraged to follow their routine clinical strategies to minimize procedural risks. These guidelines are merely to help physicians to prevent adverse events, recognize risks especially is very small children and treat appropriately.

5.5.1 Standard Risk Minimization Strategies

Standard risk minimization strategies include:

- I. Cardiologists with training and education in pediatric cardiology and with expertise in using the Amplatzer Piccolo Occluder device to close PDAs
- II. Prior experience with transcatheter closure procedures using similar devices with a minimum of 10 cases in subjects < 2 kg.
- III. Institutions will have the necessary infrastructure to support studyprocedures:

Confidential

- a. Cardiac catheterization lab or NICU bedside capability to perform intra-procedural echocardiography and fluoroscopy
- b. Anesthesiology support, as needed
- c. Catheterization laboratory, operating room, post anesthesia recovery, intensive care and step down unit spaces to accommodate cases with and without complications
- d. On-site emergency cardiac surgery services
- e. Adequate monitoring for each clinical investigation site
- f. Conducting the clinical investigation in accordance with the study, all applicable laws and regulations and any conditions of approval imposed by the appropriate IRB or applicable regulatory authorities where the clinical investigation is performed
- g. Preparation of the device and implant procedure in accordance with the device IFUs
- h. Training of Investigators both on the study protocol and implant procedure
- i. All site staff will participate and complete a raining module
- j. Implanting physicians with no prior successful transcatheter PDA closure experience in small infants (<2 kg) will receive proctoring for a minimum on one case.
- k. Assessment of continuing safety of subjects in the clinical investigation by an independent Clinical Events Committee (CEC).
- 1. Physicians are required to follow The American Heart Association Recommendations for endocarditis prophylaxis during the clinical study.
- m. Sites should follow patients per their standard of care for any reported adverse events.

5.5.2 Specific Risk Minimization Strategies for Subjects < 2kg

The following measures should also be taken to reduce the risks at the time of the procedure:

- a. The use of heparin is optional in children < 2 kg in order to decrease the risk of bleeding.
- b. Implanting physicians with no prior successful transcatheter PDA closure experience in children<2 kg will be trained on the Amplatzer Piccolo Occluder device, specifically device size selection and placement, to reduce the risk of device embolization, partial obstruction of the aorta or pulmonary artery and hemolysis which could be potentially caused by the device.
- c. The physicians will be instructed to use their clinical judgement to monitor subjects for potential adverse events related to nickel and to report such events with the goal of protecting the welfare of the subject if the root cause of the adverse event is determined to be nickel related, paying special attention to subjects weighing < 2 kg.
- d. Physicians are encouraged to utilize an anterograde implant approach, while avoiding the need for arterial access in children < 2 kg.
- e. Acquisition of invasive hemodynamic measurements is not required in children < 2 kg unless there is suspicion for pulmonary hypertension in order to minimize complication and shorten procedure time.

f. Device implant is recommended to be performed based on echocardiographic and fluoroscopic guidance with judicious utilization of intravenous contrast agents as necessary for best imaging of the PDA.

5.5.3 Aortic or Pulmonary Artery Stenosis

If stenosis of the aorta or pulmonary artery is suspected or noted during the procedure or during follow-up, the following measures are recommended:

- a. Perform a ortic catheterization to obtain invasive measurement of the gradient if the mean gradient by echocardiogram in the aortic isthmus is \geq 20mmHg.
- b. If aortic catheterization is contraindicated, then an alternative imaging study, such as computed tomography (CT) aortic angiography imaging or magnetic resonance (MR) aortic angiography imaging may be utilized.
- c. CT aortic angiography or MR aortic angiography may be used to confirm a significant aortic obstruction whenever there is \geq 50% diameter narrowing at the aortic isthmus.
- d. Alternatively, a clinical exam may be used to confirm aortic obstruction.
- Exam criteria = 1) Diminished lower extremity pulses or a blood pressure discrepancy of ≥ 20mmHg between the upper and lower extremities AND 2) an abnormal abdominal aortic Doppler pattern (blunted profile with diminished upstroke, holo-diastolic antegrade flow, or flow reversal during diastole).
- f. If a new significant gradient in the pulmonary artery or the aorta is identified on follow-up echocardiograms, a lung perfusion scan or CT/MR/aortic catheterization will be required to determine if the result meets the secondary endpoint.

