3.1 Inclusion Criteria

To participate in this clinical study, subjects must meet all of the following inclusion criteria:

- a. Diagnosis of a PDA
- b. Clinical indication for transcatheter PDA closure (discretion of the physician)
- c. Weight < 2 kg at the time of device implant

All participating study sites must obtain center specific IRB approval to enter patient data in the case reporting form (CRF) which will be called the PDA module. Individual consents from the subjects (or legally authorized representative) is not required unless local laws and governing IRB requirements require obtaining informed consent for data entry to this registry. No deviation of standard clinical practice is expected for participating in this study. No special pre-procedure, post-procedure, and follow-up testing is required for the purpose of this clinical study.

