5.6 Risk-to-Benefit Rationale

Risks associated with participating in this clinical study are not anticipated to be any different from risks associated with participating in any other large web-based registry. There is a small risk of a loss of confidentiality and every effort will be made to prevent this type of breach. The potential benefit of participating in this clinical study will allow for a large data registry to be compiled. Advantage of having this registry will include the possibility of future prospective, observational and cohort studies. The PDA module, though initially for the Amplatzer Piccolo Occluder device, will also provide a method for tracking and oversight for all PDA device procedures in the United States.

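### Section 5.5.3 item f makes a confirmatory test a requirement for classifying the secondary endpoint, which conflicts with the protocol's no-study-testing, consent, risk, schedule and endpoint text

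*Protocol*

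**What the plan says.** Protocol section 5.5.3 deals with suspected or observed stenosis of the aorta or pulmonary artery. Its list opens with "the following measures are recommended". Item f, triggered by a new significant gradient on a follow-up echocardiogram, says that "a lung perfusion scan or CT/MR/aortic catheterization will be required to determine if the result meets the secondary endpoint". The purpose it gives is classification of the endpoint.

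Other parts of the protocol describe a study that adds no testing:

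- Sections 3.1, 4 and 4.1 all carry the same sentence: "No special pre-procedure, post-procedure, and follow-up testing is required for the purpose of this clinical study".
- Section 4.1 adds: "No special consents are required for the purpose of this clinical study". Section 3.1 says that individual consent "is not required unless local laws and governing IRB requirements require obtaining informed consent for data entry to this registry".
- Section 5.6 says that participation risks "are not anticipated to be any different from risks associated with participating in any other large web-based registry". The one specific risk it names is confidentiality: "There is a small risk of a loss of confidentiality".
- Section 5.5, the parent of 5.5.3, describes its contents as guidelines to help physicians and encourages sites to keep to their routine clinical strategies.
- Appendix E, which section 4.4 gives as the schedule of all assessments, lists no perfusion scan, CT, MR or follow-up catheterization.

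The opening of section 5, by contrast, refers to additional tests required by the investigation and says that their risks have been analysed and incorporated in the sections that follow.

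**The concern.** A test required in order to settle a study endpoint is follow-up testing for the purpose of the study. Item f and the sentence in sections 3.1, 4 and 4.1 cannot both hold.

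Two things are at stake.

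- **Protection of the infants.** Some of the tests in item f involve radiation or catheterization. The default of no study-specific consent stands beside the no-testing statement in sections 3.1 and 4.1, and the risk statement in 5.6 describes a data registry. A site following item f as written would be doing protocol-directed testing that those statements do not cover.
- **Uniform ascertainment of the secondary endpoint.** A site that follows item f confirms its echo findings. A site that follows section 3.1 tests only as routine care dictates and classifies on echo when nothing else exists. The pooled obstruction rate then mixes two ways of counting.

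**Working it through.** The point rests on wording and no figure in the protocol depends on it, so the check sets the passages side by side.

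1. **Item f against its own list.** The lead-in recommends and item f requires. Section 5.5 adds that the material is guidance. The force of item f is therefore unclear within 5.5.3 itself.

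2. **Item f against the testing statement.** Items a to e concern suspected stenosis and do not mention the endpoint. Item f alone ties a test to the secondary endpoint, which puts it in direct conflict with sections 3.1, 4 and 4.1.

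3. **Item f against the schedule.** Neither Appendix E nor the follow-up list in section 4.4 contains any of the tests, even as conditional assessments. Yet section 8.1 defines a deviation as failure to follow the protocol's requirements. If item f is a requirement, omitting the test could be recorded as a deviation although the schedule never asked for it.

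4. **Item f against the endpoint definition.** Sections 2.2 and 7.3 and Appendix A define left pulmonary artery obstruction as under 30% flow to the left lung on perfusion scan, or an echo peak gradient of at least 35 mmHg if no scan is available. They define aortic obstruction as a gradient of at least 20 mmHg by catheterization, or an echo mean gradient of at least 20 mmHg if catheterization is not available. So the endpoint can be classified on echo. CT and MR appear in item f but nowhere in this definition.

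5. **Consequence for the rate.** Assume that a significant gradient in item f means one at or above the echo thresholds in step 4; item f does not say. An infant with a left pulmonary artery echo gradient of 35 mmHg or more and left-lung flow of 30% or more is an event if no scan is done and a non-event if one is. Among infants flagged by echo, classification on echo counts all of them and classification on the confirmatory test counts all or fewer. Under this assumption, for the same infants, a site that confirms can report a rate equal to or lower than one that does not, never higher.

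6. **Item f against the consent and risk text.** Where consent is obtained, sections 3.1 and 4.1 describe it as covering data entry and the sharing of health information; they do not mention testing. Section 5.6 names no test-related risk, although the opening of section 5 says that the risks of additional tests are dealt with in the sections below it.

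7. **How many infants.** The protocol gives no rate of new significant gradients and no share of them that would go untested in routine care. The number affected cannot be derived from it.

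**The case against.** The strongest reply is that item f is one loosely worded guideline. It sits under a lead-in that recommends, inside a section that calls itself guidance. Section 5.5.1 item m has sites follow reported adverse events by their standard of care, and the schedule omits the tests. The trigger is a new gradient next to an implanted device, which is a clinical finding in its own right, and items a to d already point to catheterization, other imaging or examination when stenosis is suspected. On this reading, little or no testing is added by the study.

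Much of that stands. It makes the force of item f uncertain and means that some of the testing would happen anyway. It does not remove the words of item f, which state a requirement and give the endpoint as its reason.

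A reader might infer more than the documents support:

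- **That item f mandates an irradiating or invasive test.** It offers alternatives, and MR is neither irradiating nor a catheterization.
- **That infants are entered without consent.** The absence of study consent is a default. Every site needs IRB approval, and consent is obtained where local law or the IRB requires it.
- **That the protocol declares confidentiality to be the only risk.** Section 5.6 equates the risk with that of other registries and names confidentiality; it does not say that nothing else exists.
- **That a count of exposed infants follows from an assumed gradient rate applied to the 500 subjects.** Such a count would include infants who would be worked up clinically in any case, so it would not measure added exposure.

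**Conclusion.** The inconsistency is real and should be corrected. The protocol both requires a test for an endpoint purpose and says that the study requires no special testing. Its lead-in, guideline, schedule, endpoint, consent and risk passages do not agree with item f, and the opening of section 5 adds a further conflicting statement.

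The size is not quantifiable from the protocol. It is confined to infants with a new significant gradient on follow-up echo and, among them, to those for whom testing would differ between routine care and item f. The secondary endpoint is a descriptive rate, so no power or error-rate consequence follows. The effect on counting in step 5 rests on the assumption that item f uses the endpoint's echo thresholds. The conflict in wording does not depend on that assumption. The documents do not show that any infant would be tested only because of the study; they show that a site could reasonably read the protocol either way.

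**What to change.** Reconcile sections 2.2 and 7.3 (with the matching definition in Appendix A), 3.1, 4, 4.1, the opening of 5, 5.5, 5.5.3 including its lead-in and item f, 5.6 and Appendix E, so that they state one position.

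- If the confirmatory test is a study requirement, the no-testing statements, the consent text, the risk statement and the schedule must be changed to match, and IRBs notified.
- If the study is purely observational, item f must not read as a study requirement, and the endpoint is classified from the tests done in routine care under the stated definition. The reference at the opening of section 5 to additional required tests must then be changed too.

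Which clinical rule to keep is for the sponsor and the IRBs; this review takes no position on it. The cost is protocol wording and IRB notification. The planned 500 subjects and the planned estimate (a proportion with a 95% confidence interval) need not change.

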5.6 Risk-to-Benefit Rationale

Risks associated with participating in this clinical study are not anticipated to be any different from risks associated with participating in any other large web-based registry. There is a small risk of a loss of confidentiality and every effort will be made to prevent this type of breach. The potential benefit of participating in this clinical study will allow for a large data registry to be compiled. Advantage of having this registry will include the possibility of future prospective, observational and cohort studies. The PDA module, though initially for the Amplatzer Piccolo Occluder device, will also provide a method for tracking and oversight for all PDA device procedures in the United States.

